**Table 2: Clinical Safety Laboratory Panels**

Hematology	Serum Chemistry	Urinalysis (dipstick)

 
WBC with differential (including neutrophils, basophils, eosinophils, lymphocytes, monocytes)
 
hemoglobin
 
hematocrit
 
platelet count
 
MCV
 
	
 
albumin
 
amylase
 
alkaline phosphatase
 
ALT
 
AST
 
bicarbonate
 
BUN
 
calcium
 
chloride
 
creatinine
 
GGT
 
glucose (random)
 
magnesium
 
phosphorous
 
potassium
 
sodium
 
total bilirubin
 
total protein
 
TSH
 
	
 
appearance
 
color
 
pH
 
specific gravity
 
ketones
 
leukocytes
 
protein
 
glucose
 
bilirubin
 
urobilinogen
 
occult blood (microscopic examination of sediment will be performed only if the results of the urinalysis dipstick evaluation are positive)
 

Coagulation		

 
PT
 
INR
 
APTT
 
		
Serum pregnancy test (women of childbearing potential)		Virology screen

 
βHCG
 
		
 
HIV 1 and 2 antigen/antibody combination immunoassay
 
HBV surface antigen
 
HCV RNA testing
 

WBC = white blood cell count; PT = prothrombin time; INR = international normalized ratio; APTT = activated partial thromboplastin time; ALT = alanine aminotransferase; AST = aspartate aminotransferase; BUN = blood urea nitrogen; GGT = gamma glutamyl transferase; MCV = mean corpuscular volume; TSH = thyroid stimulating hormone; βHCG= β human chorionic gonadotropin; HIV = human immunodeficiency virus; HBV = hepatitis B virus; HCV = hepatitis C virus

1. In the case of grade 3-4 laboratory abnormalities, and any clinically significant lab findings which potentially meet the definition of DLT, repeat tests must be performed every 1-2 days in order to verify duration accurately and observe recovery.

## LIST OF ABBREVIATIONS

AE	adverse event(s)
ANC	absolute neutrophil count
AST	aspartate aminotransferase
CDC	Center for Disease Control
CFR	Code of Federal Regulations
CMO	chief medical officer
CNS	central nervous system
CR	complete response
CRA	clinical research associate (monitor)
CRF	case report form
CRO	clinical research organization
CT	computed tomography
CTLA-4	cytotoxic T-lymphocyte-associated protein 4
DET	dose escalation teleconference
DLT	dose-limiting toxicity
DNA	deoxyribonucleic acid
DOR	duration of response
ECG	electrocardiogram
ECOG	Eastern Cooperative Oncology Group
eCRF	electronic case report form
EMEA	European Medicines Agency
FDA	Food and Drug Administration
FFPE	formalin-fixed paraffin-embedded
GCP	good clinical practice
HBV	hepatitis B virus
HCV	hepatitis C virus
HgB	hemoglobin
HIPAA	Health Insurance Portability and Accountability Act
HIV	human immunodeficiency virus
 I	iodine-123
ICF	informed consent form
ICH	International Conference on Harmonization
IFN	interferon
INR	International Normalized Ratio
IRB	Institutional Review Board
irRC	immune-related response criteria
irRECIST	adaptation of RECIST for immune oncology
IT	intra-tumoral
IV	intravenous
mAbs	monoclonal antibody(ies)
MHC	major histocompatibility complex
MTD	maximum tolerated dose

MV	measles virus
NCI-CTCAE	National Cancer Institute Common Terminology Criteria for Adverse Events
NE	not evaluable
NIS	human thyroidal sodium iodide symporter
NSCLC	non-small cell lung cancer
ORR	objective response rate
PD	progressive disease; pharmacodynamic(s)
PD-1	programmed cell death-1
PD-L1	programmed cell death ligand-1
PE	physical exam
PET-CT	positron emission tomography
PFS	progression free survival
PI	principal investigator
PK	pharmacokinetic(s)
PPD	purified protein derivative
PS	performance status
RECIST	response evaluation criteria in solid tumors
RNA	ribonucleic acid
RT-PCR	reverse transcription polymerase chain reaction
SAE(s)	serious adverse event(s)
SAP	statistical analysis plan
SGOT	serum glutamic oxaloacetic transaminase
SOP	standard operating procedure
SPECT-CT	single photon emission computed tomography
SUSAR	suspected unexpected serious adverse reaction
99m Tc	technetium-99m
TCID 50	median tissue culture infective dose
TIL	tumor-infiltrating lymphocyte
ULN	upper limit of normal
USPI	United States prescribing information

## 5. BACKGROUND AND RATIONALE

### 5.1. MV-NIS

Vyriad is developing the investigational medicinal product MV-NIS, which is an oncolytic measles virus (MV). The MV is a spherical, enveloped, negative-strand RNA virus that is antigenically monotypic with only one serotype, and is being developed for the treatment of oncological conditions.

MV-NIS is a recombinant, replicating, measles virus strain derived from the highly attenuated Edmonston strain of measles vaccine, MVEdmtag (Dingli 2004). The MVEdmtag strain incorporates two acquired mutations in the viral P gene encoding the V-protein, which prevents the MV mediated inhibition of the target cell type I interferon response (Dingli 2004; Ohno 2004). Among the surface proteins, the H-protein is critical to facilitate attachment of the measles virus to the receptors, CD46, SLAM and nectin-4 (Dorig 1993; Tatsuo 2000; Nielsen 2001; Noyce 2011). The other membrane protein, F-protein allows not only for cell fusion once MV attaches to the cell but also fusion with uninfected neighboring cells. The NIS gene encodes for the human thyroid sodium iodine symporter and was cloned into the MVEdmtag strain to improve non-invasive monitoring of the location and proportion of infected cells (Dai 1996; Dingli 2004). The NIS gene was cloned downstream of the hemagglutinin (H) gene (Dingli 2004). Expressed NIS actively imports iodide into cells, with sodium gradients driving cellular uptake. Expression of the NIS gene can be used as an imaging transgene to monitor viral infection. This allows use of gamma camera, single photon emission computed tomography (SPECT), or positron emission tomography-CT (PET-CT) for *in vivo* monitoring of viral replication following administration of  $^{123}\text{I}$  or  $^{99\text{m}}\text{Tc}$  isotopes.

#### 5.1.1. MV-NIS Nonclinical Toxicology

MV-NIS nonclinical toxicology has been characterized in multiple species using a variety of dosing regimens. Details are provided in the current version of the Investigator's Brochure.

#### 5.1.2. Clinical Experience with MV-NIS

The safety of MV-NIS as a monotherapy has been demonstrated in numerous clinical trials. Moreover, several patients have experienced a disease response or stabilization. Preliminary studies of immune responses in patients receiving MV-NIS therapy suggest some patients develop T cell responses to measles antigens and known tumor antigens suggesting that in addition to the tumor cell death elicited by viral mediated oncolysis, MV-NIS promotes the generation of systemic antitumoral immune responses. Details are provided in the current version of the Investigator's Brochure.

### 5.2. Safety Profile of MV-NIS

To date, 16 patients have received intraperitoneal MV-NIS at doses of  $10^8$  or  $10^9$  TCID50 and 45 patients have received IV MV-NIS at doses of  $10^6$  to  $10^{11}$  TCID50. Twelve patients have received MV-NIS intrapleurally at doses from  $10^8$  to  $9 \times 10^9$  TCID50. The highest dose levels in all three routes of administration were recommended for further study. Six patients have received MV-NIS  $10^8$  TCID50 intratumorally with one DLT.

The most common related AEs (>1 patient) with intraperitoneal administration were all grade 1 and 2, in order of descending frequency: abdominal pain (50%), fatigue (37.5%), fever, neutropenia, leukopenia and flatulence (all at 19%), nausea, diarrhea and abdominal distension (all at 12.5%). There were no DLTs.

In the IV study, related grade 1-2 AEs seen in at least 5 patients were: nausea (n=10); chills and leukopenia (each n=8); fever (n=6); and diarrhea and neutropenia, (each n=5). Grade 3-4 AEs deemed at least possibly related to protocol therapy were: neutropenia (n=10); thrombocytopenia (n=5); anemia (n=2); and lymphopenia (n=1). One patient treated with cyclophosphamide and TCID50 9x10^7 had a grade 3 left ventricular failure possibly related to therapy. One grade 4 neutropenia was considered a DLT at the highest dose level (10^11 TCID50).

With intratumoral administration the only toxicities observed in more than one patient were anorexia, fatigue (both 33%) and lymphopenia (50%). There was 1/6 DLTs (grade 3 oral cavity fistula in non-injected tumor).

With intrapleural administration the most frequent toxicities were hematological including anemia, thrombocytopenia, leukopenia and neutropenia. There were no DLTs reported.

The [Investigator's Brochure](#) contains a summary of all MV-NIS-related AEs reported to date across the clinical trials, irrespective of route of administration.

## 5.3. Rationale

### 5.3.1. Study Rationale

The therapeutic efficacy of transgenic, vaccine strain-MV has been demonstrated using both *in vitro* and *in vivo* models of various solid tumors and hematologic malignancies. Pre-clinical data is available for hematologic and solid malignancies including, but not limited to, ovarian cancer ([Peng 2002](#); [Hasegawa 2006](#)), glioblastoma multiforme ([Phuong 2003](#)), breast cancer ([McDonald 2006](#)), multiple myeloma ([Peng 2001](#); [Dingli 2004](#)), lymphoma ([Grote 2001](#)), hepatocellular carcinoma ([Blechacz 2006](#)), prostate cancer ([Msaouel 2009b](#)), and mesothelioma ([Li 2010](#)).

Programmed cell death-1 (PD-1) and programmed death ligand-1 (PD-L1) are two of the many immunologic checkpoints that regulate the immune response with clinically available mAbs for the treatment of advanced cancers, including non-small cell lung cancer (NSCLC). Currently, two anti-PD-1 antibodies, nivolumab and pembrolizumab, and one anti-PD-L1 antibody, atezolizumab, are FDA approved in advanced or metastatic NSCLC. Checkpoint blockade with PD-(L)1 inhibitors is one of the most promising forms of cancer immunotherapy that improves the capacity of the immune system to acknowledge and delete tumors. While a subset of advanced NSCLC patients benefits from PD-(L)1 blockade, unfortunately a majority of patients do not respond to single agent checkpoint inhibition. Therefore, new therapeutic approaches that expand the available endogenous anti- tumor T cell repertoire or increase the tumor cell antigenicity for T cell recognition are rational therapeutic agents to be combined with checkpoint inhibition. Available clinical trial data shows that oncolytic therapy with MV-NIS is well tolerated, and several patients have experienced a disease response or stabilization. Preliminary studies of immune responses in patients receiving MV-NIS therapy suggest some patients develop improved T cell responses to measles antigens and known tumor antigens. In conclusion, our preclinical data utilizing NSCLC cell lines, multiple published preclinical reports on the

successful combination of oncolytic viral therapy and PD-1/PD-L1 axis blockade, acceptable safety and toxicity data from available clinical trials, and preliminary immune response data from patients receiving MV- NIS, support the combination of intra-tumoral MV-NIS with PD-L1 blockade in a clinical trial setting for patients with advanced NSCLC.

Study VYR-MV1-101 is a Phase 1 study designed to determine the maximum tolerated dose (MTD) and toxicity of attenuated MV-NIS virus combined with atezolizumab in patients with recurrent and metastatic NSCLC. The study will further evaluate safety, clinical and immune responses in an expansion cohort of 18 additional patients with NSCLC.

### **5.3.2. Rationale for Dosage Selection**

Routes of administration relevant for this protocol in terms of determining an appropriate starting dose include intratumoral, intraperitoneal and intrapleural routes. Studies have been conducted at pleural doses up to  $9 \times 10^9$ , peritoneal doses up to  $10^{11}$  and IT doses up to  $10^8$  TCID50 with no MTD reached to date.

Taking a conservative approach, the lowest of these doses already used in the clinic is proposed as the starting dose for this study.

## 6. STUDY OBJECTIVES

### 6.1. Primary Objectives

- To determine the MTD of the intra-tumoral administration of an Edmonston strain MV genetically engineered to produce NIS, in combination with the PD-L1 inhibitor atezolizumab in patients with recurrent and metastatic NSCLC.

### 6.2. Secondary Objectives

- To describe the safety and toxicity of the intra-tumoral administration of MV-NIS with atezolizumab.
- To assess preliminary antitumor efficacy by following:
  - radiographic objective response rate (ORR)
  - duration of response (DOR)
  - progression-free survival (PFS)

... in the injected lesion, non-injected lesions and overall, per RECIST 1.1.

### 6.3. Exploratory objectives

- To determine the time-course of viral infection, dissemination, and elimination through the measurement of NIS gene expression using SPECT/CT imaging.
- To assess viremia, viral replication, and viral shedding/persistence following intra-tumoral administration of MV-NIS and immunotherapy.
- To obtain preliminary data regarding the antitumor efficacy by serial measurements of radioiodine uptake by SPECT/CT, radiological ORR, DOR and PFS and to correlate with PD-L1 expression and other immune biomarkers.
- To characterize the peripheral blood immune phenotype, presence and peripheral blood repertoire representation of neoantigen-specific T cells, and cell-free DNA of patients at potential immunologic transition points including study enrollment, therapy initiation, during therapy, and at follow-up.
- To evaluate if therapy with MV-NIS, atezolizumab, or both alters the peripheral blood immune phenotype, presence and peripheral blood repertoire representation of neoantigen-specific T cells, or cell-free DNA.
- To characterize the tumor microenvironment by immunohistochemistry (IHC) for PD-L1 and other immune markers of interest on tissue prior to and at the completion of MV-NIS injection and following atezolizumab treatment.
- To evaluate if MV-NIS alter the pretreatment tumor microenvironment levels of PD-L1 or immune markers after therapy in the lesion injected with MV-NIS.
- To determine if lesions not injected with MV-NIS express comparable levels of PD-L1 or contain an immune marker milieu within the tumor microenvironment similar to the lesion injected with MV-NIS after treatment with MV-NIS and atezolizumab.

- To assess if changes to the circulating or tumor microenvironment immune biomarkers associate with clinical response.
- To evaluate the tumor genomic mutational burden by whole exome sequencing, level of neoantigen expression and signal transduction pathways by RNAseq prior to and after therapy with MV-NIS and atezolizumab.
- To determine if changes to the tumor genomic mutational burden, level of neoantigen expression or alterations in signal transduction pathways are associated with clinical response
- To assess the secondary efficacy parameters (ORR, DOR and PFS) using irRECIST in addition to classical RECIST 1.1.
- To compare PFS of the combination of MV-NIS and atezolizumab in patients with recurrent and metastatic NSCLC versus historical controls
- To evaluate if the combination of intra-tumoral MV-NIS and atezolizumab results in improved ORR and DOR when compared to historical controls of patients treated with atezolizumab as a single agent.

## 7. INVESTIGATIONAL PLAN

### 7.1. Overview of Study Design

This is a phase 1, dose escalation study of the combination of intra-tumoral MV-NIS and systemic atezolizumab in patients with recurrent and metastatic NSCLC. After the dose escalation phase of the trial, a dose expansion cohort will further investigate safety, clinical and immune responses at the MTD. [Figure 1](#) shows the study design. The study will involve 9-24 patients in the escalation phase and 15-18 in the expansion cohort, to provide a total cohort of 21 patients for efficacy evaluation at the MTD.

#### 7.1.1. Dose escalation

MV-NIS will be administered once intra-tumorally, to a single tumor, with a 21-gauge needle, Quadrafuse®, or other suitable needle using ultrasound or CT guidance on day 1 of treatment in 3 escalating dose cohorts, starting at dose level 1 (Table 3).

**Table 3: MV-NIS Dose Levels**

Dose Level	Number of viruses
-1	$3 \times 10^7$
1	$1 \times 10^8$
2	$3 \times 10^8$
3	$1 \times 10^9$

Atezolizumab will be given per the US prescribing information ([Tecentriq® USPI 2016](#)) at 1200 mg IV on day 15 and then every 3 weeks thereafter until progression of disease, discontinuation due to toxicity, or withdrawal of consent.

#### 7.1.1.1. DLT definition

DLT will be defined as an AE that is not pre-existing due to malignancy, attributed (definitely, probably, or possibly) to the MV-NIS, occurring within 36 days of MV-NIS administration and meeting the following criteria:

Hematologic:	$\geq$ grade 3 as per NCI Common Terminology Criteria for Adverse Events (CTCAE) v4.03 except grade 3 ANC lasting < 72 hours.
Renal:	Serum creatinine $\geq$ 2 times baseline.
Viremia:	Lasting for $\geq$ 4 weeks after intratumoral injection.
Clinical measles:	Any grade per CDC definition ( http://www.cdc.gov/measles/hcp/index.html )
Other non-hematologic, including:	$\geq$ grade 3 AE as per NCI CTCAE v4.03.
• Allergic reactions	
• Autoimmune toxicity	
• Organ toxicity	

Note: in the case of grade 3-4 laboratory abnormalities, and any other clinically significant lab findings which potentially meet the definition of DLT, repeat tests must be performed every 1-2 days in order to verify duration accurately and observe recovery.

AEs meeting these definitions but related only to atezolizumab will not be considered a DLT.

### **7.1.2. Conduct of escalation cohorts**

A standard 3+3 design will be used for the dose escalation part of the study. Starting at dose level 1 (refer to [Table 3](#)), three patients will be treated per dose level. The first three patients treated at dose level 1 will be enrolled at least 24 hours apart. All patients will be observed for a DLT period of 36 days after MV-NIS administration (which is 3 weeks after atezolizumab) and the last patient in each cohort must have completed the DLT period prior to each dose escalation decision. Resolution of viremia in all patients at a dose level is required prior to dose escalation being allowed.

If a DLT is observed, 3 additional patients will be enrolled at that dose level. If 1/6 patients experiences DLT, escalation may proceed; if  $\geq 2/6$  patients experience DLT, the MV-NIS dose will be de-escalated and 3 further patients added at the previous dose level. Dose level -1 will only be explored if dose level 1 is not tolerated. Doses will not be escalated in any individual patient. Any patient who experiences a DLT will be taken off study drugs, but will be followed up for response and PFS.

If no DLTs are seen at any of the dose levels, then the MTD will be the maximum delivered dose ( $1 \times 10^9$ ). MTD will be defined as the highest safely administered dose at which no more than one out of six or 0/3 patients experience DLT.

The first 6 patients of the expansion cohort will be enrolled and observed for 36 days after the 6th patient has received treatment prior to any additional patients being treated. If  $\leq 1/6$  DLT is observed then the remaining patients will be enrolled and treated sequentially, with no waiting period or limitation on simultaneous enrolment. If  $\geq 2/6$  patients in the expanded cohort experience a DLT, then the entire expansion cohort will be re-enrolled at the next lower dose level.

If a patient fails to complete the initial course of therapy (defined as study drug administration and four weeks of observation) for reasons other than adverse events or disease progression based on the day 36 CT-scan, then the patient will be regarded as non-evaluable for DLT and an additional patient will be treated at the current dose level. However, all AE information from patients who received any study treatment will be utilized in the analysis.

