### **8.5. Replacement of Patients in Study**

A patient who discontinues from the trial during the active treatment for reasons other than AE/SAE, or disease progression can be replaced.

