## **12. STUDY ASSESSMENTS AND PROCEDURES**

Once Vyriad has confirmed a cohort slot availability, an informed consent must be obtained before any study-specific samples are taken or study-specific tests or evaluations are conducted. Screening assessments should be performed within 21 days before the IT dose of study drug is administered on Day 1. Study eligibility will be based on satisfying all of the study inclusion and exclusion criteria for each cohort.

Study Day 1 is defined as the date the study drug is administered via IT injection, with subsequent study days numbered sequentially thereafter.

If significant changes from baseline are noted during the course of the study, additional unscheduled clinic visits may be undertaken by the investigator, or requested by the sponsor, in order to determine both the relevance of the finding(s) and the duration of the event(s).

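### DLT evaluability rests on four weeks of observation against a 36-day DLT window, and the plan does not say how patients who leave early count in the 3+3 and first-6 decisions

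*Combined protocol and SAP*

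**What the plan says.** The DLT definition (Section 7.1.1.1 and synopsis) counts MV-NIS-attributed events "occurring within 36 days of MV-NIS administration and meeting the following criteria". Section 7.1.2 repeats the window: "All patients will be observed for a DLT period of 36 days after MV-NIS administration". It adds that this is three weeks after atezolizumab, which is first given on day 15.

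Evaluability is decided by a different period. In Section 7.1.2 and the synopsis, a patient is non-evaluable, and another is treated, if the initial course is not completed "for reasons other than adverse events or disease progression based on the day 36 CT-scan". That course is "defined as study drug administration and four weeks of observation". Atezolizumab is not named.

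Section 8.5 has a second rule: a patient who discontinues during active treatment "for reasons other than AE/SAE, or disease progression can be replaced". It has no Day 36 limit.

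The safeguards are these. Section 7.1.2 requires the last patient in a cohort to complete the DLT period, and viremia to resolve in all patients at the dose, before escalation. The first-6 expansion gate waits 36 days after the sixth patient is treated. Section 9.1.7.1 keeps visits going after study drug is stopped. Section 8.4 ends all data collection on study withdrawal. Section 13.1.1 defines safety, PK/PD and efficacy populations, but no DLT-evaluable set.

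**The concern.** Every escalation decision, and the primary objective, rests on a count of DLTs among three or six patients. The dose sought is for the combination, so a patient informs the count only after receiving both agents and being observed through the window, or after having a DLT. The written rule asks for less in three ways.

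- It is satisfied at about Day 29, so a patient lost on Days 29 to 35 has completed the course.
- Its adverse-event exception covers any adverse event. A patient who leaves on Day 12 for an event not attributed to MV-NIS, or later for an atezolizumab-only event (which by definition is not a DLT), is not declared non-evaluable.
- Its progression exception refers to a Day 36 scan, which cannot explain a failure to complete four weeks. Section 8.5 places leavers for any progression outside replacement.

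If such a patient stays in the denominator and was not followed, the unobserved time can only lower the DLT count. With cohorts this small, one patient matters.

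**Working it through.** **1. The plan's own figure.** Day 1 is the injection: "Study Day 1 is defined as the date the study drug is administered via IT injection". Atezolizumab is given "at 1200 mg IV on day 15 and then every 3 weeks thereafter". Day 15 + 21 = Day 36, so the statement that the window ends three weeks after atezolizumab reproduces.

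**2. The evaluability period.** Day 1 + 28 = Day 29. That covers 29 − 15 = 14 of the 21 days after atezolizumab and stops 36 − 29 = 7 study days before Day 36 (8 days if 36 elapsed days are meant).

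**3. What may be recorded for an early leaver.** Adverse events are collected to 30 days after the last dose. A patient who received only MV-NIS reaches that limit on Day 1 + 30 = Day 31, five days before Day 36. Section 12.1.17 stops routine collection sooner if new treatment starts, although known events judged possibly related should still be reported. As the table was extracted, Table 1 schedules no hematology or chemistry between Day 8 and Day 36. Viremia is tested on Days 3 and 15, then on Day 36 only if Day 15 is positive, although one DLT criterion is viremia lasting at least four weeks.

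**4. Effect on escalation.** The protocol gives no operating characteristics for the 3+3 part, so the DLT rates, hazard shape and number of truncated patients below are assumptions.

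- Escalation needs 0/3, or 1/3 followed by 0/3: P(esc) = P(0/3) + P(1/3) × (1 − P)³, where P is the true 36-day DLT rate.
- A patient seen for t days under a constant hazard shows a DLT with probability r = 1 − (1 − P)^(t/36).
- With one such patient among the first three: P(0/3) = (1 − r)(1 − P)² and P(1/3) = r(1 − P)² + (1 − r) × 2P(1 − P). The second three are fully observed.

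At P = 0.33:

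- Full follow-up: 0.3008 + 0.4444 × 0.3008 = 0.434.
- One patient to 28 days, r = 0.268: 0.3288 + 0.4440 × 0.3008 = 0.462.
- One patient to 14 days, r = 0.144: 0.3842 + 0.4432 × 0.3008 = 0.517.

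At P = 0.50:

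- Full follow-up: 0.1250 + 0.3750 × 0.125 = 0.172.
- One patient to 28 days, r = 0.417: 0.1458 + 0.3958 × 0.125 = 0.195.
- One patient to 14 days, r = 0.236: 0.1909 + 0.4409 × 0.125 = 0.246.

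**5. Sensitivity to when risk falls (P = 0.33).**

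- Early risk: assume 75% of the hazard falls by day 14 and the rest evenly to day 36. For 14 days, r = 1 − 0.67^0.75 = 0.259 and P(esc) = 0.466. For 28 days the exponent is 0.75 + 0.25 × 14/22 = 0.909, r = 0.305 and P(esc) = 0.445.
- Late risk: assume all hazard follows atezolizumab. For 28 days, r = 1 − 0.67^(14/21) = 0.234 and P(esc) = 0.477. For a patient who leaves before atezolizumab, r = 0 and P(esc) = 0.582.

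**6. First-6 expansion gate (P = 0.33).** With one truncated patient, P(≤1/6) = 0.67⁵ + (1 − r) × 5 × 0.33 × 0.67⁴ = 0.135 + (1 − r) × 0.3325. This is 0.358 with full follow-up, 0.378 with one 28-day patient and 0.420 with one 14-day patient (constant hazard).

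**The case against.** The strongest reply is that Section 7.1.2 already requires 36 days of observation for everyone, holds escalation until the last patient completes the window, and requires viremia to resolve. Stopping drug does not stop visits, and the safety committee reviews cumulative data and may decline to escalate. A leaver whose event meets the criteria and is at least possibly attributed to MV-NIS is a DLT, not a missing observation. All of this stands and narrows the problem to patients whose follow-up is actually cut short by withdrawal, loss or death. None of it says how such a patient is counted.

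A reader might infer that anyone who progresses early stays evaluable. Section 7.1.2 does not support that: it exempts only progression on the Day 36 scan, so on its literal wording a Day 12 progressor is non-evaluable. Only Section 8.5, a general replacement rule, leaves earlier progression unreplaced. What stands is that the two sections disagree.

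A reader might also infer that the plan scores incomplete patients as having no DLT. No section says so. It follows only because the rules use counts alone, and an evaluable patient without a recorded DLT has nowhere else to go.

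The wording is also open to kinder readings. The synopsis uses study drug for either agent, while Section 12 uses it for the injection. The start of the four weeks is not stated; counted from atezolizumab they would end on Day 15 + 28 = Day 43 and cover the window. A rule that needs such a reading should be made explicit. Section 8.5 would permit replacing a patient lost on Days 29 to 35 for other reasons, but does not require it.

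**Conclusion.** The point holds as an inconsistency between the evaluability rule and the DLT window, together with an adverse-event exception wider than the DLT definition. Applied as written, it can leave an incompletely observed patient in the 0/3, 1/6 and first-6 counts as an implicit non-DLT.

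The size for the quoted mismatch is modest: one 28-day patient adds about 3 percentage points to the chance of escalating at a true rate of 33% (43% to 46%) or about 2 at 50% (17.2% to 19.5%). One 14-day patient adds about 8 and 7 points. These rest on assumed DLT rates, a constant hazard and one truncated patient. The effect is smaller if risk is early, which is plausible for a single Day 1 injection, and larger if risk follows atezolizumab.

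It would be too strong to conclude that the escalation is biased in practice or will select too high a dose. The documents do not say how many patients will be incomplete, and the safeguards lower that number. For a counted patient with missing time, however, the error runs only towards escalation.

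**What to change.** Reconcile the synopsis and Sections 7.1.1.1, 7.1.2 and 8.5, and add a DLT-evaluable set to Section 13.1.1. For dose escalation and the first-6 gate, a patient is evaluable who either had a DLT, or received the assigned MV-NIS dose and the first atezolizumab dose and was observed through the full 36-day window. Replace all other patients for these decisions, whatever the reason for leaving, and keep them in the safety and efficacy populations.

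The cost is a few aligned sentences, an occasional replacement patient and a slightly slower cohort. No dose or clinical management rule changes.
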